| No Exercise + Atorvastatin | 24 |
| No Exercise + Placebo | 24 |

Randomization is stratified by:

1. Sex (male/female)
2. Prior active statin treatment (yes/no)

Block sizes are concealed from investigators. Randomization codes are securely stored and revealed only after database lock.

11. Sample size calculations

Sample-size calculations were prespecified for the primary mechanistic contrast (Exercise + Placebo vs Exercise + Atorvastatin) for the primary endpoint (Δ CS) and the key secondary endpoint (Δ VO_{2peak}).

Power calculations (as prespecified in the published protocol) used prior training data (Sjúrðarson *et al.*, 2022a, 2022b): mean $\Delta\text{CS} \approx 25 \mu\text{mol}\cdot\text{g}^{-1}\cdot\text{min}^{-1}$, SD $\approx 18 \mu\text{mol}\cdot\text{g}^{-1}\cdot\text{min}^{-1}$, and a target between-group difference of $17 \mu\text{mol}\cdot\text{g}^{-1}\cdot\text{min}^{-1}$, consistent with attenuation magnitudes reported previously (Mikus *et al.*, 2013). For $\text{VO}_{2\text{peak}}$, we assumed $\Delta \approx 3.6 \pm 3.3 \text{ mL}\cdot\text{kg}^{-1}\cdot\text{min}^{-1}$ and targeted a $3.0 \text{ mL}\cdot\text{kg}^{-1}\cdot\text{min}^{-1}$ between-group difference.

Final enrolled sample size.

A total of $N = 120$ participants were randomized (36 per exercise arm; 24 per non-exercise arm). The primary mechanistic comparison—Exercise + Placebo vs Exercise + Atorvastatin—is effectively a two-group contrast, and power calculations were therefore based on the two exercise groups.

Using the effect-size assumptions prespecified in the published protocol, the achieved sample provides:

- **Citrate synthase (CS) activity:**
 - With full enrollment ($n = 36$ per group), power is approximately 97–98% to detect a $17 \mu\text{mol}\cdot\text{g}^{-1}\cdot\text{min}^{-1}$ difference (SD ≈ 18).
 - With 10% attrition (≈ 33 per group), power remains high at ≈ 94 –95%.

- **$\text{VO}_{2\text{peak}}$:**
 - With full enrollment ($n = 36$ per group), power is approximately 96–97% to detect a $3.0 \text{ mL}\cdot\text{kg}^{-1}\cdot\text{min}^{-1}$ difference (SD ≈ 3.3).
 - With 10% attrition (≈ 33 per group), power remains ≈ 93 –95%.

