12.1 Statistical Hypotheses

The primary mechanistic hypothesis is that supervised exercise training increases skeletal-muscle CS activity and that concomitant high-dose atorvastatin attenuates this response.

The key secondary hypothesis is that concomitant atorvastatin treatment attenuates training-induced improvements in cardiorespiratory fitness, assessed as the between-group difference in change in VO_{2peak} between Exercise + Placebo and Exercise + Atorvastatin.

For the primary endpoint (ΔCS), six pre-specified pairwise contrasts will be evaluated to characterize exercise, statin, and combined effects:

| No. | Comparison | Scientific question |
|-----|--|--|
| 1 | Exercise + Placebo > Exercise + Atorvastatin | Does atorvastatin blunt exercise-induced mitochondrial gains? (Primary contrast) |
| 2 | Exercise + Placebo > No Exercise + Atorvastatin | Benefit of exercise alone vs. drug alone |
| 3 | Exercise + Placebo > No Exercise + Placebo | Absolute effect of exercise training |
| 4 | Exercise + Atorvastatin > No Exercise + Atorvastatin | Can exercise mitigate potential statin-related attenuation? |
| 5 | Exercise + Atorvastatin > No Exercise + Placebo | Combined treatment vs. no intervention |
| 6 | No Exercise + Placebo > No Exercise + Atorvastatin | Do statins alone affect mitochondrial function? |

Contrasts are listed in the hypothesized direction for interpretation; all tests will be two-sided.

13. Statistical interim analyses and stopping guidance

No interim analyses for efficacy are planned. No early stopping guidelines were specified.

14. Timing of final analysis

Data collection is considered complete after the last participant's last visit. Analyses will begin only after:

1. all data have been entered and cleaned,
2. all queries have been resolved, and
3. The randomization code has been formally unblinded following database lock.

No unblinded interim looks are permitted before database lock.

15. Timing of outcome assessments

Primary and secondary outcomes are measured at V1 (baseline) and V2 (12 weeks). Blood samples and questionnaire data are collected at V1, week 6, and V2.

Section 4: Statistical principles

16–18. Confidence Intervals, P-values, and Multiplicity

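### Contrast 4 is labelled as a test of whether exercise mitigates a statin effect, but it estimates only the training effect among people taking atorvastatin

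*SAP*

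**What the plan says.** Section 12.1 states the primary mechanistic hypothesis: training raises citrate synthase (CS) activity and "concomitant high-dose atorvastatin attenuates this response". Attenuation in that sentence means a smaller training response.

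The table that follows sets out six pairwise contrasts and pairs each with a scientific question. Three matter here:

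- Contrast 1, Exercise + Placebo against Exercise + Atorvastatin, is the primary contrast and asks whether the drug blunts the training gain.
- Contrast 4, Exercise + Atorvastatin against No Exercise + Atorvastatin, asks "Can exercise mitigate potential statin-related attenuation".
- Contrast 6, No Exercise + Placebo against No Exercise + Atorvastatin, asks "Do statins alone affect mitochondrial function".

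Below the table the SAP adds: "Contrasts are listed in the hypothesized direction for interpretation; all tests will be two-sided". Section 12 places all six contrasts in one Holm–Šidák family at a two-sided familywise 0.05 and reserves superiority claims for contrasts that pass. Nothing links the reading of contrast 4 to the result of contrast 1 or contrast 6.

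**The concern.** The table says in advance what each multiplicity-controlled result will be taken to mean. For contrast 4 that meaning does not match the estimand. Atorvastatin is common to both arms, so the difference is the simple effect of training among statin users. A working training programme makes it positive whether or not the drug harms anything.

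At stake is the wording of a confirmatory conclusion. Read as labelled, an ordinary training effect would be reported as evidence that exercise offsets a statin effect, in a trial that may have found no such effect.

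**Working it through.** **Inputs from the SAP.** Section 11: training gain in CS about 25, target difference between the exercise arms 17, SD about 18 (all in µmol·g⁻¹·min⁻¹); 36 per exercise arm and 24 per non-exercise arm. Section 12: six tests, Holm–Šidák, familywise 0.05.

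**Assumption not in the SAP.** Mean change is zero in both non-exercise arms. It is varied below for No Exercise + Atorvastatin, because contrast 6 is listed in the direction of a fall there, with no size given.

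**The SAP's own figure first.** For contrast 1, SE = 18 × √(1/36 + 1/36) = 4.24 and 17/4.24 = 4.01. Two-sided noncentral-t power at 0.05 with 70 df is 97.7%, which agrees with the stated 97–98%. The SAP states no power for contrast 4.

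**Contrast 4 taken singly.** SE = 18 × √(1/36 + 1/24) = 4.74, 58 df. The strictest Šidák step uses alpha = 1 − 0.95^(1/6) = 0.0085.

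| True contrast 4 | Ratio to SE | Power at 0.05 | Power at 0.0085 |
|---|---|---|---|
| 25 − 0 = 25 (no statin effect) | 5.27 | 99.9% | 99.3% |
| (25 − 17) − 0 = 8 (targeted attenuation) | 1.69 | 38.2% | 16.0% |

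**Contrast 4 within the family.** All six contrasts were simulated (100,000 trials, SD 18, pooled variance). The k-th smallest p-value is adjusted as 1 − (1 − p)^(7 − k), with a running maximum. A contrast counts as positive when its adjusted p is below 0.05 in the listed direction. Mean changes are in the order Exercise + Placebo, Exercise + Atorvastatin, No Exercise + Atorvastatin, No Exercise + Placebo.

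| Mean changes | True contrast 4 | Contrast 4 positive | Contrast 1 positive | Contrast 6 positive |
|---|---|---|---|---|
| 25, 25, 0, 0 (no statin effect) | 25 | 99.8% | 1.3% | 1.3% |
| 25, 13, 0, 0 | 13 | 64.5% | 68.4% | 1.3% |
| 25, 8, 0, 0 (target of 17) | 8 | 24.7% | 94.1% | 1.2% |
| 25, 8, −4, 0 | 12 | 55.5% | 94.6% | 7.1% |
| 25, 8, −8, 0 | 16 | 83.0% | 95.2% | 24.7% |
| 25, 8, −17, 0 | 25 | 99.8% | 96.5% | 86.7% |
| 25, 0, 0, 0 (complete blunting) | 0 | 0.9% | 100% | 0.9% |

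**Sensitivity.** With 10% attrition (33 and 22 per arm) the first and third rows give 99.5% and 22.3% for contrast 4. Over SD 14 to 22 they give 100% to 96.8% and 43% to 15%.

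In the first row contrast 4 is almost always positive while contrasts 1 and 6, which do compare drug with placebo, are almost never positive. In the first and sixth rows contrast 4 has the same true value, 25, although atorvastatin does nothing in one and lowers CS by 17 with and without exercise in the other. Contrast 4 cannot tell these two states apart.

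**The case against.** The strongest reply is that the test itself is sound. A superiority claim on contrast 4 means that Exercise + Atorvastatin exceeds No Exercise + Atorvastatin, which is a valid statement. No sentence in the SAP says that a positive contrast 4 licenses a mitigation claim. The label says the attenuation is potential, and contrasts 1 and 6 are reported alongside with confidence intervals. Read as asking whether training still raises CS despite the drug, contrast 4 is the right comparison. All of this stands, and it limits the point to the question attached to the contrast. It does not rescue the label, because asking whether training works in statin users is a different question from asking whether it offsets a statin effect.

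Two stronger readings are tempting, and the SAP does not support them:

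- **That contrast 4 is unlikely to be positive when attenuation is as large as targeted, so the test runs against its label.** The 24.7% holds only with zero change in No Exercise + Atorvastatin. The SAP gives no value for that arm, and a fall of 4 already lifts the figure above one half. The 16.0% at alpha 0.0085 is lower still, but it describes only the strictest step; the step-down procedure usually rejects contrasts 1 to 3 first. And if the drug does remove most of the training response, a smaller contrast 4 is a correct answer about statin users.
- **That a mitigation claim should be allowed whenever contrast 6 is also positive.** This replaces loss of the training response, which is how section 12.1 words attenuation, with a statin effect at rest. With changes of 25, 8, 0, 0 contrast 6 is truly null and positive in 1.2% of trials, so the rule would open in about 1% although the drug removed 17 of 25 units. Even with a true resting fall of 8, contrast 6 is positive in only 24.7%.

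**Conclusion.** The concern holds as a mismatch between the estimand of contrast 4 and the question assigned to it. The mismatch follows from the design and needs no numerical assumption, since both arms take atorvastatin. Its practical size is clearest when the drug has no effect: about 99.8% of trials would answer the labelled question with a yes when there is nothing to mitigate. That figure rests on the SAP's gain of 25 and SD of 18 and on no change in the non-exercise arms, and it stays at about 97% or more up to SD 22.

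How often contrast 4 is positive under the targeted attenuation is not settled by the SAP. It runs from about 25% to 99.8% as the change in No Exercise + Atorvastatin goes from 0 to −17. The two-sided test, the Holm–Šidák control and the place of contrast 4 in the family are not at fault.

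**What to change.** In the section 12.1 table, replace the question for contrast 4 with *Effect of exercise training in people taking atorvastatin*. Add one interpretation sentence below the table, for example: *A positive contrast 4 alone does not support a claim that exercise mitigates a statin effect; attenuation of the training response is judged from contrast 1, and a statin effect without exercise from contrast 6.* Do not add a rule that makes a mitigation claim depend on contrast 6 alone.

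The cost is table wording and one sentence. No test, alpha, model or sample size changes. What is given up is the option of reporting contrast 4 by itself as evidence of mitigation, which it cannot supply.

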All secondary and exploratory outcomes, including $\text{VO}_{2\text{peak}}$, will be analyzed using the same general model framework, with emphasis on effect estimates and 95% confidence intervals; p-values will be reported without multiplicity adjustment and should not be used to infer definitive treatment effects.

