| Variable | Total (n =) | Exercise + Atorvastatin | Exercise + Placebo | No Exercise + Atorvastatin | No Exercise + Placebo |
|--------------------------|-----------------|----------------------------|-----------------------|----------------------------------|--------------------------|
| Demographics | | | | | |
| Sex (M/F) (n (%)) | | | | | |
| Age (years) | | | | | |
| Anthropometry | | | | | |
| Height cm | | | | | |
| Weight kg | | | | | |
| BMI kg·m ⁻² | | | | | |
| Waist circumference (cm) | | | | | |
| Hip circumference (cm) | | | | | |
| Body fat (%) | | | | | |
| Lean mass (kg) | | | | | |

| | | | | | |
|--|--|--|--|--|--|
| Cardiorespiratory | | | | | |
| VO _{2peak} (mL·min ⁻¹) | | | | | |
| VO _{2peak} (mL·kg ⁻¹ ·min ⁻¹) | | | | | |
| Resting heart rate (BPM) | | | | | |
| Systolic BP (mmHg) | | | | | |
| Diastolic BP (mmHg) | | | | | |
| Metabolic profile | | | | | |
| Fasting glucose (mmol/L) | | | | | |
| HbA _{1c} (mmol/mol) | | | | | |
| Fasting insulin (pmol/L) | | | | | |
| Fasting c-peptide (pmol/L) | | | | | |
| HOMA-IR | | | | | |
| Lipids (total, LDL, HDL, TG) mmol/L | | | | | |
| Apolipoproteins (A-I, A-II, B etc.) | | | | | |
| Muscle biochemistry | | | | | |
| Citrate synthase activity ($\mu\text{mol}\cdot\text{g}^{-1}\cdot\text{min}^{-1}$) | | | | | |
| 3-HAD activity ($\mu\text{mol}\cdot\text{g}^{-1}\cdot\text{min}^{-1}$) | | | | | |
| PFK activity ($\mu\text{mol}\cdot\text{g}^{-1}\cdot\text{min}^{-1}$) | | | | | |
| Clinical and patient- reported | | | | | |

| | | | | | |
|------------------------------|--|--|--|--|--|
| SF-36 (total and subdomains) | | | | | |
| SAMS scores (0–10) | | | | | |

Section 6: Analysis

26. Outcome definitions

Primary outcome

- *Citrate-synthase maximal activity* ($\mu\text{mol}\cdot\text{g}^{-1}\cdot\text{min}^{-1}$), measured in skeletal-muscle homogenates by fluorometry.

The primary endpoint is the change from baseline (V1) to 12-week follow-up (V2).

Key secondary outcome

- *Maximal oxygen uptake (VO_{2peak})* ($\text{mL}\cdot\text{kg}^{-1}\cdot\text{min}^{-1}$), assessed during an incremental cycling test to exhaustion.

The key secondary endpoint is the change from V1 to V2.

Additional secondary outcomes

Unless otherwise specified, outcomes refer to the within-participant change (V2 – V1).

They include (but are not limited to) variables in the following domains:

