1. **Cardiorespiratory and hemodynamic:** VO_{2peak} (absolute), steady-state VO_2 , resting HR, systolic and diastolic BP.
2. **Body composition and anthropometry:** body weight, fat %, lean mass (BIA), waist/hip circumference.
3. **Lipid and lipoprotein profile:** total, LDL, HDL, triglycerides, lipoprotein(a), apolipoproteins (A-I, B-100 etc.), CETP, LCAT, albumin, transthyretin.
4. **Glucose metabolism and insulin sensitivity:** fasting glucose, insulin, HbA_{1c} , HOMA-IR, Matsuda index, ISR, oral disposition index.

5. **Muscle biochemistry and mitochondrial function:** 3-HAD, PFK, CoQ10, intramuscular atorvastatin (CoQ10 and intramuscular atorvastatin will be quantified only where sufficient muscle tissue is available after primary analyses).
6. **Patient-reported outcomes:** SF-36 (total + subdomains), SAMS (severity & type).
7. **Exploratory outcomes:** anaerobic capacity (Wingate), systemic biomarkers (CoQ10, CRP, cytokines), white-blood-cell count, telomere length, PFAS, hemoglobin mass (CO-rebreathing), targeted / untargeted muscle proteomics, RPE (training/testing).

Note: Detailed laboratory and assay procedures (e.g., DIA-PASEF, UHPLC-MS) are specified in the main protocol. Outcome definitions may be refined based on data quality and scientific relevance before database lock.

27. Analysis method

Analyses will primarily follow the intention-to-treat (ITT) principle (see Section 20), with complementary per-protocol (PP) analyses assessing efficacy under adherence conditions.

Primary Analysis

All continuous outcomes will be analyzed using constrained mixed models, with inherent baseline adjustment (all participants will be put in the same group at baseline). The model will include group (four arms), time (V1/V2; categorical), group × time interaction, sex (male/female), and prior active statin treatment (yes/no) as fixed effects and will be specified with an unstructured covariance pattern to account for repeated measurements on each participant and use the Satterthwaite approximation for degrees of freedom. Model residuals and fitted values will be inspected, and right-skewed outcomes may be log-transformed.

Supplementary analysis

- **Per-protocol analysis:** conducted in the predefined PP population (see Section 20) to estimate efficacy under adherence conditions.
-

28. Handling Missing Data

Missingness may occur due to withdrawal, assay failure, or QC exclusion.

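### Intramuscular atorvastatin is sent to the four-arm V1/V2 model with no exception; there the fit may fail, or the standard error between the two atorvastatin arms may be too small (minor)

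*SAP*

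**What the plan says.** Section 26 (Additional secondary outcomes, domain 5) lists "3-HAD, PFK, CoQ10, intramuscular atorvastatin". The only special rule is that CoQ10 and intramuscular atorvastatin "will be quantified only where sufficient muscle tissue is available after primary analyses". The default form of the outcome is set just above: "Unless otherwise specified, outcomes refer to the within-participant change" from V1 to V2. Section 15 has secondary outcomes measured at both visits.

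Section 27 then states: "All continuous outcomes will be analyzed using constrained mixed models, with inherent baseline adjustment". The model has four arms, two visits and one shared baseline mean, and it "will be specified with an unstructured covariance pattern". Nothing says that the covariance may differ by arm. Section 27 adds that "right-skewed outcomes may be log-transformed", with no rule for zeros or values below a quantification limit. Section 12 repeats the scope: secondary outcomes "will be analyzed using the same general model framework, with emphasis on effect estimates and 95% confidence intervals". Sections 16–18 promise between-group differences in change with 95% CIs for every outcome.

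Section 9 stops lipid-lowering therapy for four weeks before baseline, completes V1 before randomization and gives two of the four arms placebo.

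**The concern.** The general model assumes an outcome that varies at both visits, with a similar spread in all arms. The concentration of the study drug in muscle is not such an outcome. By design, nobody should have been taking atorvastatin in the four weeks before V1, and half of the participants receive none up to V2. Three of every four expected values (120 at V1 and 60 of 120 at V2) should therefore lie at or near zero.

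The informative comparison for this analyte is between the two arms that take the drug, because only there can one see whether training changes muscle exposure. The same pair, "Exercise + Atorvastatin > No Exercise + Atorvastatin", is contrast 4 in Section 12.1, listed there for CS. In the common model its standard error borrows the V2 variance of the placebo arms, which says nothing about variation among treated participants. At stake is a 95% CI that is too narrow for that one comparison, or a model that cannot be fitted and has no named replacement.

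**Working it through.** The SAP gives no figure for this outcome, so there is none to reproduce.

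**Inputs.** From the SAP: arm sizes 36 (Exercise + Placebo), 36 (Exercise + Atorvastatin), 24 (No Exercise + Atorvastatin) and 24 (No Exercise + Placebo); the model of Section 27. Assumed, because the SAP does not say: V1 and placebo V2 values near zero, V1 unrelated to V2, one covariance for all arms. The treated-arm SDs s1 (exercise) and s2 (no exercise), the placebo-arm SD sP and the tissue yield are varied below.

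**Case 1: every V1 value is zero, or replaced by one constant.** The V1 residual variance is then zero. With N = 120, the V1 part of the log-likelihood is −120 × ln(SD at V1), which grows without limit as that SD shrinks. Evaluated on simulated data it was −39 at SD 1 and 2,172 at SD 1e-8. The rise of 2,211 agrees with 120 × ln(1e8) = 2,210. There is no maximum, and a generalised least squares fit in R stopped with a false-convergence error.

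**Case 2: values small but not zero, raw scale, common covariance.** V1 then carries almost no information on V2, so the contrast rests on the pooled V2 variance:

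pooled variance = (35·s1² + 23·s2² + 58·sP²) / 116

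model SE² = pooled variance × (1/36 + 1/24)

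true SE² = s1²/36 + s2²/24

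With s1 = s2 = 1 and sP ≈ 0, the pooled variance is 58/116 = 0.50. The model SE is √(0.50 × 0.0694) = 0.186 and the true SE is √0.0694 = 0.264. The ratio is 0.707, so the SE is 29% too small. Coverage is 2Φ(1.96 × ratio) − 1 = 83%.

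| Assumption | Pooled variance | SE ratio | SE too small by | Coverage |
|---|---|---|---|---|
| Equal treated SDs, sP ≈ 0 | 58/116 = 0.50 | 0.707 | 29% | 83% |
| s1 = 2, s2 = 1 | 163/116 = 1.405 | 0.799 | 20% | 88% |
| s1 = 1, s2 = 2 | 127/116 = 1.095 | 0.625 | 37% | 78% |
| sP half the treated SD | 72.5/116 = 0.625 | 0.791 | 21% | 88% |
| Tissue from 75% of treated (27, 18), all placebo | 43/101 = 0.426 | 0.652 | 35% | 80% |
| Tissue from all treated, 75% of placebo | 58/101 = 0.574 | 0.758 | 24% | 86% |

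Simulation of the full constrained model agrees for the first row: mean model SE 0.186 against a true 0.264 over 300 REML fits (coverage about 86%), and SE ratio 0.695 with coverage 82% over a larger set of runs. One R fit gave 0.179 against 0.254 from the two arms alone, a ratio of 0.706.

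**Other contrasts in the first row's setting.** Exercise + Placebo vs Exercise + Atorvastatin: model SE² = 0.50 × 2/36 = 1/36, the true value, so the ratio is 1.00. Exercise + Placebo vs No Exercise + Atorvastatin: √(0.50 × 0.0694 × 24) = 0.91. Exercise + Atorvastatin vs No Exercise + Placebo: √(0.50 × 0.0694 × 36) = 1.12.

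**Log scale.** The log SD is √ln(1 + CV²). Take a treated CV of 60% (0.555) and let the near-zero values have an assay-noise CV of 20%, 30%, 60% or 100% (0.198, 0.294, 0.555, 0.833). The ratio √[(1 + (noise SD/treated SD)²)/2] is then 0.75, 0.80, 1.00 and 1.28. Simulated type I error runs the same way: 13–15%, 11–12%, 5–6% and about 1%.

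**Alternative.** V2 compared between the two atorvastatin arms only held its nominal level in simulation (about 5%).

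**The case against.** The strongest reply is that the 29% rests on several conditions that the SAP does not state: values near but not at zero, raw scale, a common covariance, equal treated-arm SDs and equal tissue yield. That is right, and a single figure should not be quoted without its range. On the log scale, which the SAP permits, the error may vanish or turn conservative. That stands too, although exact zeros have no logarithm and the SAP has no rule for them.

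The SAP also requires inspection of residuals and lets outcome definitions be refined before lock. Two arms with almost no spread at V2 would be conspicuous, and a failed fit could mislead nobody. But neither provision names a replacement model, and because analysts stay blinded to allocation until lock (Section 9), a check by arm would come after it. The protocol may also restrict which arms or visits are assayed. It is not at hand, and the SAP's own rule contains no such restriction.

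A reader might infer that the trial's main results are at risk, or that the SAP asks whether training alters muscle drug exposure. Neither is supported. CS and VO2peak do not have this structure. Contrast 4 is pre-specified for CS only; the exposure question is what this analyte can answer, not one that the SAP poses. Section 12 also says that secondary p-values are not definitive, so the width of the CI matters here more than the type I error.

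**Conclusion.** The point holds, as a minor one. The SAP assigns this outcome to a model that its own design makes unsuitable. The consequence depends on the data: a visible failure to fit if V1 is constant, or, on the raw scale with a common covariance, a standard error between the two atorvastatin arms that is too small by about 29% in the reference case and by 20–37% when one treated-arm SD is twice the other. Unequal tissue yield at 75% gives 24–35%. A covariance allowed to differ by arm would cure the standard error but not the failed fit, and the SAP does not specify one.

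It would be too strong to say that the reported interval will be 29% too narrow, or that the error always runs in that direction. The near-zero values are an inference from the wash-out and placebo, and the log-scale result depends on assay noise that the SAP does not give. With equal SDs and equal tissue yield, the Exercise + Placebo vs Exercise + Atorvastatin contrast for this analyte is also unaffected. Only one tissue-limited, non-confirmatory secondary outcome is concerned.

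**What to change.** In Section 27, exempt intramuscular atorvastatin from the four-arm change model. Compare V2 between Exercise + Atorvastatin and No Exercise + Atorvastatin only, by linear regression of log concentration on arm, sex and prior statin treatment, with a 95% CI. Name in advance one method that still gives an estimate and CI if values fall below the quantification limit, for example a censored log-normal regression. A rank test alone would not serve, because Section 12 puts the emphasis on estimates and intervals. Summarise V1 and the placebo arms descriptively.

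The cost is two or three sentences before database lock and no extra data. The downside is that this outcome then has no model-based statin-vs-placebo estimate.

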Additional pre-specified pairwise comparisons among the four groups will be analyzed to fully characterize exercise, drug, and combined effects (see Section 12).

Key secondary objective.

To evaluate changes in VO_{2peak} ($\text{mL}\cdot\text{kg}^{-1}\cdot\text{min}^{-1}$) across the four groups, with the same principal contrast (Exercise + Placebo vs Exercise + Atorvastatin), testing whether atorvastatin blunts training-induced adaptations in VO_{2peak} .

For details on outcome selection and rationale, see the published protocol.

Section 3: Study Methods

9. Trial design

This investigator-initiated, randomized, double-blinded (medication) and placebo-controlled trial evaluates the effects of high-dose atorvastatin and supervised high-intensity interval training (HIIT), alone or combined, over 12 weeks in adults with dyslipidaemia. Participants are allocated to one of four parallel arms:

1. Exercise + Placebo
2. Exercise + Atorvastatin
3. No Exercise + Atorvastatin
4. No Exercise + Placebo

Medication allocation is double-blinded (participants and investigators). Exercise allocation cannot be blinded to participants or trainers; however, outcome assessors and laboratory personnel will remain blinded to medication allocation, and data analysts will remain blinded to both medication and exercise allocation until database lock.

Interventions

- **Wash-out:** 4-week discontinuation of lipid-lowering therapy before baseline (week 0).
- **Medication:** Atorvastatin 40 mg (Week 1-2), then 80 mg daily; matching placebo in placebo arms.
- **Exercise:** Supervised high-intensity interval training (HIIT) three times per week, performed at or above 90 % of maximal aerobic power (MAP), with intensity monitored using power output (wattage), heart rate (HR), and ratings of perceived exertion (RPE).
- **Non-exercise arms:** Maintain habitual physical activity.

Study visits:

V0 = Screening, V1 = Baseline (all measurements completed before randomization), Week 6 = mid-intervention blood samples and questionnaires, V2 = Post-intervention (12 weeks).

10. Randomization

Randomization uses a computer-generated list prepared by an independent statistician. Allocation is performed by a non-involved colleague after completion of baseline assessments. Participants are randomized in a 60:40 exercise:non-exercise ratio to achieve approximately:

| Group | n |
|-----------------------------------|----------|
| Exercise + Placebo | 36 |
| Exercise + Atorvastatin | 36 |

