Analyses will assume that outcome data are missing at random (MAR) conditional on observed data included in the analysis model. Missing data will be handled implicitly in the constrained mixed model using maximum likelihood estimation. The extent and reasons for missingness will be summarized by group.

Sensitivity analyses

Sensitivity analyses for the primary outcome (CS activity) and the pre-specified secondary outcome (VO_{2peak}) may be conducted if dropout exceeds 10% in any randomization group to assess robustness to missing-data assumptions. In such cases, simple plausibility-bound scenarios may be applied (e.g., baseline value carried forward). These analyses are intended as plausibility bounds rather than definitive MNAR analyses; confirmatory inference for ΔCS will remain based on the prespecified LMM under the MAR assumption; VO_{2peak} sensitivity results will be interpreted descriptively.

29. Additional analyses (supportive/exploratory)

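### Section 27 models only V1 and V2, so week-6 values of outcomes measured then are left out of the missing-data handling; a three-level time factor is a cheap improvement

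*SAP*

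**What the plan says.** Section 27 sets the scope, "All continuous outcomes will be analyzed using constrained mixed models", and the time factor: "The model will include group (four arms), time (V1/V2; categorical), group × time interaction". The covariance is unstructured, and all groups share one baseline mean.

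Section 15 places primary and secondary outcomes at V1 and V2, then adds: "Blood samples and questionnaire data are collected at V1, week 6, and V2". The visit list in Section 9 agrees: "Week 6 = mid-intervention blood samples and questionnaires". Section 26 defines outcomes as the V2–V1 change unless stated otherwise, and Sections 16–18 report V2–V1 changes and contrasts for all outcomes.

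Section 28 treats outcome data as "missing at random (MAR) conditional on observed data included in the analysis model" and handles missing values only through the likelihood of that model. It adds: "The extent and reasons for missingness will be summarized by group". Its sensitivity analyses are optional and cover only CS activity and VO2peak.

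**The concern.** The two-level model fits the endpoint. What it loses is information about participants who have a week-6 value but no V2 value. By the wording of Section 28, the missing-at-random assumption conditions only on what is in the model, and week 6 is not in it.

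The outcomes concerned are those repeated at week 6. The SAP does not name them; by inference they include lipids, glucose markers, SF-36 and SAMS severity. Early response or muscle symptoms could plausibly influence whether a participant returns for V2. If they do, and the arms differ in week-6 level or in dropout mechanism, the V2–V1 contrast is biased. These outcomes have no other stated safeguard: a summary of reasons for missingness describes the problem but does not adjust for it. Section 12 rests their interpretation on estimates and confidence intervals, which is where such bias would show.

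**Working it through.** **Plan's own figures.** No stated figure is in dispute. The main design figure reproduces: CS, difference 17, SD 18, 36 per arm, two-sided 0.05 gives 97.7% power (stated 97–98%). It does not depend on week 6.

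**Inputs.** From the SAP: 36 participants per exercise arm and a 10% attrition scenario (Section 11). Assumed: unit SD; a true effect of 0.5 SD at week 6 and V2; correlations in the order V1–week 6 / V1–V2 / week 6–V2; dropout log-odds slope of 1, 2 or 3 per SD of the week-6 value; 10% dropout in the atorvastatin arm.

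**Mechanism.** With correlations 0.3/0.3/0.7, the slope of V2 on week 6 given V1 is (0.7 − 0.3 × 0.3)/(1 − 0.3²) = 0.61/0.91 = 0.670. If dropout shifts the mean week-6 value, adjusted for V1, among those still observed, about 0.67 of that shift passes into the V2 mean of the two-level model. A bias of 0.055 SD needs a shift of about 0.055/0.670 = 0.082 SD. The three-level model uses the week-6 values of everyone and so corrects it.

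**Bias.** Large-sample simulation (2,000,000 per arm). Estimates from the V1/V2 model for slopes 1/2/3, true value 0.500:

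| Correlations | Timing of dropout | Same rule in both arms | Atorvastatin arm only |
|---|---|---|---|
| 0.3/0.3/0.7 | all after week 6 | 0.483/0.460/0.449 | 0.445/0.413/0.399 |
| 0.3/0.3/0.7 | half before, unrelated to outcome | 0.490/0.476/0.468 | 0.471/0.451/0.442 |
| 0.5/0.5/0.7 | all after week 6 | 0.488/0.472/0.462 | 0.460/0.436/0.424 |
| 0.6/0.55/0.7 | all after week 6 | 0.488/0.475/0.467 | 0.466/0.446/0.436 |
| 0.6/0.55/0.7 | half before, unrelated to outcome | 0.494/0.484/0.479 | 0.482/0.469/0.464 |

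The three-level model gives 0.501 in the first two rows. Repeat runs of the first and fourth rows at 1,000,000 per arm agreed to within 0.004 and gave 0.496–0.502 for three levels.

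For scale, the SE of the contrast with 36 vs 36 is √(2(1 − 0.3²)/36) = 0.225 SD. In the first row the bias is 0.017–0.051 SD with a shared rule (0.08–0.23 SE) and 0.055–0.101 SD in one arm only (0.24–0.45 SE).

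**No true effect** (0.3/0.3/0.7). Bias is 0.000–0.001 under a shared rule, and −0.056/−0.087/−0.102 if only the atorvastatin arm is affected.

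**Other assumptions.** A separate simulation (36 per arm, slope 1.5 in one arm, correlations 0.5/0.5/0.6 to 0.7/0.6/0.8) gave a bias of about 0.05 SD at 10% dropout and 0.08–0.09 SD at 20%, against less than 0.005 SD with three levels. With complete V2 data the two models gave the same contrast.

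**Limit of the fix.** If the half that leaves before week 6 is also outcome-related, one-arm estimates are 0.444/0.411/0.396 with two levels and 0.473/0.458/0.450 with three. About half the bias remains.

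**Finite samples** (36 vs 36, 20,000 replicates, all dropout after week 6). RMSE, two-level vs three-level:
- shared rule: 0.235/0.233/0.234 vs 0.233/0.232/0.231, a fall of about 0.4–1.3%
- one arm only: 0.238/0.245/0.250 vs 0.231/0.231/0.231, a fall of about 3–8%

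**Precision under unrelated dropout.** The squared partial correlation of week 6 and V2 given V1 is 0.670² = 0.449. With 10% lost after week 6, the variance ratio is 1 − 0.10 × 0.449 = 0.955 and the SE ratio √0.955 = 0.977, a 2.3% gain. If half is lost before week 6, the variance ratio is 1 − 0.449 × 0.05/0.95 = 0.976 and the SE ratio 0.988, a 1.2% gain.

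**The case against.** The strongest reply is that the SAP is coherent as written. Time is V1/V2, the endpoint is V2–V1, and the reported contrasts in Sections 16–18 are V2–V1, so a longer model is a preference. This stands to the extent that the point is an improvement and not an error.

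The size is also modest. The larger figures need outcome-driven dropout confined to one arm, all of it after week 6, and a low V1–V2 correlation. Section 28 names assay failure and QC exclusion as causes of missingness, and these have no evident link to week-6 values. Section 24 encourages V2 attendance after discontinuation, and with complete V2 data nothing is gained. All of this stands.

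The affected outcomes are inferred, and Section 30 uses symptom questionnaires for harms, so week 6 may serve monitoring only. That is possible, but the SAP does not say it.

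Finally, Section 12 already rules out definitive inference for these outcomes. This limits the consequence. It is no reason to leave collected data unused when the same contrast can be estimated at least as well for almost no cost.

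**Conclusion.** The point holds as a low-cost improvement. For any continuous outcome repeated at week 6, the V1/V2 model leaves an observed on-treatment value outside the missing-data assumption. At 10% atorvastatin-arm dropout the resulting bias ranges from about 0.006 to 0.05 SD under a shared dropout rule and from about 0.02 to 0.10 SD if only that arm is affected. It is zero with complete V2 data, with dropout unrelated to outcome, or under a shared rule with no true effect. Apart from the 36 per arm and the 10% attrition, every input is an assumption, and the Gaussian figures may not carry over to the bounded 0–10 SAMS score. Estimates are not expected to move much; the case for the change is that it is nearly free. The CS and VO2peak analyses are untouched.

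**What to change.** Add to Section 27, in words such as:

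> For continuous outcomes also measured at week 6, time has three levels (V1, week 6, V2), with a common mean for all groups at V1 and a 3×3 unstructured covariance. The reported endpoint remains the between-group contrast in V2–V1. Week 6 informs the model, and any week-6 contrast is descriptive.

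If week 6 is meant only for monitoring or harms, say that instead. The sentence works without a list of outcomes; naming them in Section 15 would be a convenience. Leave CS, VO2peak, other outcomes measured only at V1 and V2, and non-continuous items such as SAMS type as they are.

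The cost is SAP wording and one extra factor level, with no new data. The downsides are a few more mean and covariance parameters, a possibly poor fit for the SAMS score, and no help for participants who leave before week 6. The choice should be fixed before database lock.
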